1.3 SCHEDULE OF ACTIVITIES

Table 1. Schedule of Activities for NDURE and Usual Care: Screening, Treatment, and Follow-up								
Study Period		Screening	Allocation	Treatment			Follow-Up	
Visit Label	Visit #			Pre -Op	Pre - D/ C	Post - D/C		
Visit Label	Visit #	1	--	2	3 ^{a,b}	4 ^c	5 ^d	6 ^e
Study Activity								
Enrollment	Eligibility Screen	X						
	Informed Consent	X						
Allocation	Allocation		X					
Study Intervention	NDURE			X	X	X	X	
	Usual Care			X	X	X	X	
Study Assessments								
Baseline	Demographics	X						
	Baseline Oncologic Characteristics	X						
	Charlson-Deyo Comorbidity Index	X						
	PORT Delay Nomogram	X						
	Lukwago Cultural Questionnaire	X						
Safety	Adverse Events			←		→		
Efficacy	Surgical Details				X			
	PORT Start Date						X	
Fidelity	NDURE Fidelity						X	
Feasibility	NDURE Accrual	X						
	NDURE Completion			X	X	X	X	
	Navigator Caseload			←		→		
	Navigator Time Allocation			X	X	X	X	
Acceptability	PSN-I Questionnaire						X	
	Semi-Structured Interview						X	
	Program Evaluation Questionnaire						X	
Barriers to Timely PORT	PBQ-Patient Questionnaire			X	X	X	X	
	PBQ-Navigator			X	X	X	X	
	Presurgical RT Consult						X	
	Pre-RT Dental Extractions						X	

Table 1. Schedule of Activities for NDURE and Usual Care: Screening, Treatment, and Follow-up								
Study Period		Screening	Allocation	Treatment			Follow-Up	
Visit Label	Visit #			Pre-Op	Pre-D/C	Post-D/C		
		1	—	2	3 ^{a,b}	4 ^c	5 ^d	6 ^e
Study Activity								
Cancer Care Delivery Processes	Date Pathology Report Returned						X	
	Date of Postoperative Referral to Radiation Oncology						X	
	Date of Postop Appointment with Radiation Oncology						X	
	Date of CT Simulation						X	
Adjuvant Therapy Details	Type of Adjuvant Therapy						X	
	PORT Completion Date						X	
	Radiation and Medical Oncology Facility						X	
Health Behavior Constructs	CTM-15 Questionnaire				X	X		
	ISEL-12 Questionnaire	X					X	
	PSQ Questionnaire	X			X	X		
	IPQ-R Consequences Questionnaire	X			X	X		
	CASE-Cancer Questionnaire	X					X	

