To explore the preliminary impact of NDURE compared with UC on completion of adjuvant therapy	PORT duration, defined as the number of days from the initiation of PORT to the completion of PORT among patients who complete the intended course of adjuvant therapy.
	Completion of intended course of PORT, defined as receipt of the planned PORT dose (total Gy)
To explore the preliminary clinical impact of NDURE compared with UC on decreasing barriers to timely PORT.	Percent of total barriers on PBQ that are resolved
	Number of unresolved barriers on PBQ
	Reason for PORT delay
To explore the preliminary behavioral mechanism of action of NDURE.	CTM-15 scale score
	Change from baseline in 
 ISEL-12 scale score Perceived Susceptibility scale score IPQ-R Consequences scale score CASE-Cancer scale score

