6 STUDY INTERVENTION

6.1 STUDY INTERVENTION ADMINISTRATION

6.1.1 STUDY INTERVENTION DESCRIPTION

6.1.1.1 NDURE

NDURE is a navigation-based, MLI targeting barriers to timely, guideline-adherent PORT at the patient-, healthcare team-, and organization-levels (Figure 3). Consistent with best practices for the development and evaluation of complex interventions,^{38,39} key NDURE functions (the intervention's basic purposes; in bold) and selected forms (specific intervention components/strategies customized to local context necessary to carry out each function) are described below.

Function 1: Navigate along the cancer care continuum.

PORT-focused navigation encounters linked to care transitions. There are three manualized navigation encounters with the NDURE navigator. Encounters occur along the cancer care continuum and are linked to key care transitions (presurgical consult, hospital discharge, postoperative clinic visit). During each encounter, the NDURE navigator delivers patient education about timely PORT, addresses challenges with transportation, assesses barriers to timely PORT, and creates or updates and implements the PORT Care Plan. Direct contact between the NDURE navigator and patient occurs via three clinic/hospital-based, face-to-face NDURE navigation encounters lasting 30-60 minutes each.

Function 2: Improve patient knowledge about Guidelines for timely PORT and associated care processes.

Form: NDURE Patient Resource Guide. During each of the three NDURE navigation encounters, the NDURE navigator uses the NDURE Patient Resource Guide to (a) educate patients +/- caregivers about NCCN Guidelines for timely PORT; (b) provide a personalized risk-estimate of PORT delay using a validated nomogram⁴⁰; (c) explain the oncologic consequences of PORT delay; and (d) describe the healthcare utilization steps necessary to start PORT (e.g. dental evaluation +/- extractions, CT simulation, etc.).⁴¹

Function 3: Minimize the burden of travel for HNSCC care.

Form: Travel Support Along the Continuum. The navigator provides patients +/- caregivers with information about travel resources, offers travel assistance through community-based programs, and provides travel-associated financial support. Travel assistance may also take the form of provision of temporary housing (e.g. American Cancer Society Hope Lodge) for patients desiring care at MUSC who cannot travel back and forth daily for 6 weeks of radiation therapy.

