6.1.2 ADMINISTRATION AND/OR DOSING

6.1.2.1 NDURE

NDURE will be delivered in one-on-one, face-to-face sessions between the navigator and the participant in a clinic- or hospital-based setting. The NDURE intervention consists of three navigation encounters (Study Visits 2-4), which are expected to take 30-60 minutes each. The NDURE navigation encounters (Study Visits 2-4) will coincide with the presurgical consult, hospital discharge, and 1st postoperative clinic visit (see Section 1.3, Schedule of Activities). These time points were chosen to facilitate case identification and coordination across key care transitions. Contact beyond the three prescribed sessions will occur with a frequency and modality (e.g. text message, email, etc.) dictated by patient and navigator need. The NDURE intervention will be delivered in the following settings: the MUSC Head and Neck Tumor Center and MUSC hospital. A single dedicated navigator with no competing clinical or administrative responsibilities outside of this trial will deliver the NDURE intervention. Full dose of the NDURE intervention will consist of completing all three navigation sessions. Because the administration schedule and dose of usual care is highly variable, the NDURE intervention will not be dose-matched to usual care on intensity, duration, and/or frequency. Participants in the trial are permitted to interact with other participants after randomization, regardless of treatment allocation. Such encounters may occur in waiting rooms before or after clinic appointments given the single-site design of the trial.

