8 STUDY ASSESSMENTS AND PROCEDURES

8.1 SCREENING PROCEDURES

Once a subject has signed the ICF, an identification number will be assigned to him/her and the study related screening procedures will start. A subject will be randomized into the study after he/she has signed the ICF and all eligibility criteria have been met.

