9.4.9 EXPLORATORY ANALYSES

For other exploratory endpoints (e.g., health behavior constructs), data will be summarized using frequency and percent for categorical variables and using mean, median, standard deviation, IQR and range for continuous variables. We will construct 90% CIs to provide a measure of uncertainty in estimated proportions and means. Comparisons between trial arms of other exploratory endpoints will be performed using *t*-tests and chi-square tests, or Wilcoxon rank sum and Fisher's exact tests as appropriate. Pre- and post-intervention values of variables measuring the theoretical constructs underlying NDURE (i.e. care coordination, self-efficacy in cancer care, support, and knowledge) will be compared using Wilcoxon sign rank tests. Comparisons between arms of the change in scores will be conducted using Wilcoxon rank sum tests.

For the exploratory endpoints of barrier reduction and unresolved barriers, we will calculate the proportion of unresolved barriers and the frequency of unresolved barriers (respectively) at the end of NDURE, consistent with prior PN studies⁵¹. We will use logistic regression to assess the association between unresolved barriers and the rate of PORT delay (primary endpoint), controlling for randomization stratification variables.

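### The patient barrier questionnaire (PBQ-P) is first taken after unblinded allocation, so the exploratory barrier endpoints lack a pre-randomization value and rest on a post-randomization denominator

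*Combined protocol and SAP*

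**What the plan says.** - **Schedule.** One table covers both arms ("Table 1. Schedule of Activities for NDURE and Usual Care: Screening, Treatment, and Follow-up", Section 1.3). Its "PBQ-Patient Questionnaire" row is blank at Visit 1 and at Allocation and marked at Visits 2, 3, 4 and 5. ISEL-12, PSQ, IPQ-R Consequences and CASE-Cancer are marked at Visit 1.
- **Allocation.** Section 8.1: "A subject will be randomized into the study after he/she has signed the ICF and all eligibility criteria have been met". The Allocation column of Table 1 lies between Visits 1 and 2. Section 4.2.1 describes the RCT as non-blinded.
- **What happens at Visit 2.** Section 6.1.2.1: "The NDURE navigation encounters (Study Visits 2-4) will coincide with the presurgical consult, hospital discharge, and 1st postoperative clinic visit". Section 6.1.1.1 gives the content of every encounter: "During each encounter, the NDURE navigator delivers patient education about timely PORT, addresses challenges with transportation, assesses barriers to timely PORT".
- **The form.** Section 8.4.5 describes PBQ-P as 17 yes/no items reported by the patient.
- **Endpoints and analysis.** Section 3, Table 2 lists as exploratory "Percent of total barriers on PBQ that are resolved" and the number of unresolved barriers. Section 9.4.9 will calculate "the proportion of unresolved barriers and the frequency of unresolved barriers (respectively) at the end of NDURE". It names no baseline covariate, and its between-arm tests for exploratory endpoints are unadjusted. The unresolved barriers also enter a logistic model for PORT delay that controls only for the stratification variables.

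**The concern.** The stated exploratory objective is that NDURE decreases barriers, yet no barrier level is recorded before patients know their arm. Two consequences follow.

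First, percent resolved divides by a total that accumulates only after randomization. Teaching patients about PORT delay and asking about barriers are parts of the intervention, so the number of barriers a patient recognises and ticks may depend on arm. A difference in percent resolved could then mix a change in what obstructs PORT with a change in what gets recorded.

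Second, the between-arm comparison of unresolved barriers cannot be adjusted for how many barriers each patient started with. The four scales collected at Visit 1 do not have this limitation.

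**Working it through.** The plan states no figure for the barrier endpoints, so there is nothing to reproduce. The check has three parts.

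**1. Order of events, from the text.** Visit 1 (no PBQ-P), then allocation, unblinded (Sections 8.1 and 4.2.1), then Visit 2, which holds NDURE session 1 (Section 6.1.2.1) and the first PBQ-P (Table 1). Visits 3 and 4 each hold an NDURE session and a PBQ-P. Visit 5, after PORT starts, holds the last PBQ-P and is not a navigation encounter. Nothing states whether the form comes before or after the session at Visits 2-4, or who hands it out. Two facts are therefore established: no PBQ-P value precedes allocation, and every barrier in the total is recorded afterwards.

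**2. How the denominator could move percent resolved.** Assume B barriers with 2 unresolved, and k extra barriers recorded because of teaching or questioning. The underlying B barriers do not change.

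- If the extras are resolved: (B - 2 + k) / (B + k)
- If the extras stay unresolved: (B - 2) / (B + k)

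| B | k | Extras resolved | Extras unresolved |
|---|---|---|---|
| 3 | 0 | 1/3 = 33.3% | 33.3% |
| 3 | 1 | 2/4 = 50.0% | 1/4 = 25.0% |
| 3 | 2 | 3/5 = 60.0% | 1/5 = 20.0% |
| 5 | 0 | 3/5 = 60.0% | 60.0% |
| 5 | 1 | 4/6 = 66.7% | 3/6 = 50.0% |
| 5 | 2 | 5/7 = 71.4% | 3/7 = 42.9% |

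The percentage can shift by 10 points or more either way. On the count, extras that are resolved leave it at 2, and extras that are not raise it to 3 or 4. B and k are assumed; the documents give neither.

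**3. Precision lost on the unresolved count.** Linear adjustment for a baseline with correlation r to the final value multiplies the variance by 1 - r².

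- r = 0.3: 1 - 0.09 = 0.91, a 9% reduction
- r = 0.6: 1 - 0.36 = 0.64, a 36% reduction

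The correlation is an assumption; the documents give none for PBQ-P.

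**The case against.** A reader might infer that the arms are measured differently, that the first PBQ-P is already contaminated, and that percent resolved is inflated in NDURE's favour. The documents do not support this.

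- PBQ-P is the same fixed checklist on the same schedule in both arms, so usual-care patients are asked the same 17 questions.
- If the form is completed before the Visit 2 session, that value precedes any navigator contact at the visit and only knowledge of allocation could affect it.
- Usual care also includes a detailed barrier assessment by the head and neck nurse navigator at intake (Section 6.1.1.2).
- The table above shows that the distortion, if any, could run in either direction. On the unresolved count, extra recording can only leave NDURE unchanged or make it look worse.

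A reader might also infer that the missing baseline biases the comparison of unresolved counts. It does not: randomization protects the unadjusted comparison, and what is lost is precision. Nor do the barrier endpoints fall short of their own definition, since Table 2 does not define them as change from baseline. CTM-15 has no baseline either.

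A denominator limited to Visit 1 barriers would do harm as the main analysis. Section 8.5.1 uses the PBQ deliberately to capture wound complications, further surgery, emergency visits and readmissions, and these cannot exist before surgery.

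All of this stands. What remains is that the order of form and session is unstated, that the forms at Visits 3-5 follow at least one scheduled NDURE session in any case, and that no pre-allocation value exists.

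**Conclusion.** The point holds as a low-cost improvement to exploratory endpoints. It is documented that PBQ-P is first taken after unblinded allocation, that this visit holds the first NDURE session, and that the order of the two is unspecified. It follows that the total-barriers denominator is entirely post-randomization and that the unresolved count has no pre-allocation covariate. Influence of the intervention on reporting is plausible, but its presence, size and direction are not known. The illustrative shifts rest on assumed barrier counts, and the 9-36% variance figure rests on an assumed correlation of 0.3-0.6. The primary endpoint comes from treatment dates in the medical record (Section 8.4.4) and is not touched.

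**What to change.** 1. **Table 1:** add PBQ-P at Visit 1, before allocation, in both arms. Keep the Visit 2 form rather than moving it.
2. **Table 1 or Section 8.4.5:** state that PBQ-P at Visits 2-4 is completed before the navigation encounter, and at the same point of the visit in usual care.
3. **Section 9.4.9, count:** compare the number of unresolved barriers between arms adjusting for the Visit 1 PBQ-P count.
4. **Section 9.4.9, percentage:** keep percent resolved over all barriers, so that post-surgical items stay in. Add a sensitivity analysis of percent resolved among barriers already present at Visit 1, in patients with at least one.

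The cost is 17 more yes/no items, a few minutes, at an existing visit. Post-surgical items will still have no baseline. The sensitivity analysis gains a denominator that arm cannot influence, but whether a barrier counts as resolved remains a post-randomization self-report. For participants already randomized the Visit 1 value cannot be recovered, and the report should state that limitation.

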
^a Study Visit 5 assessments are to be administered after the start of PORT. For the purposes of determining when to administer Study Visit 5 assessments, the study coordinator will determine that a patient has started PORT either by verifying in the EMR (for patients undergoing PORT at MUSC) or by contacting the patient no sooner than 8 weeks after surgery (for patients undergoing PORT outside of MUSC). If PORT is indicated but never initiated, Study Visit 5 assessments are to be completed 12 weeks after surgery.
 
^b Following completion of PORT, the study coordinator will gather all of the required source documentation to ascertain efficacy and cancer care delivery endpoints as well as adjuvant therapy details
							

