Function 4: Improve communication between patient and providers regarding intentions and goals for timely, guideline-adherent PORT.

Form: Standardized discussion of expected indication for PORT and choice of radiation facility at initial consultation. At the initial surgical consultation, the clinician informs the patient that based on his/her clinical stage, it is expected that treatment will include a package of surgery and PORT. At this same clinical encounter, the NDURE navigator facilitates a discussion with the patient and clinician to help the patient decide at which facility he/she will receive PORT.

Function 5: Enhance coordination of care between healthcare teams during care transitions and about treatment sequelae.

Form: NDURE PORT Care Plan. At each navigation encounter, the NDURE navigator meets with the patient, caregiver, and clinicians to generate (and update) a PORT Care Plan. The NDURE PORT Care Plan is an EMR-based document that (a) captures clinical factors and the care delivery processes necessary to start PORT; (b) describes the patient's barriers to timely PORT; and (c) documents the patient's personalized Barrier Reduction Plan.

Function 6: Restructure the organization to clarify roles and responsibilities for care processes associated with PORT delivery to avoid duplication and gaps in care.

Form: NDURE Navigator makes referrals and schedules appointments to optimize adherence with key PORT care delivery process. The NDURE navigator is assigned sole responsibility for making all PORT-related referrals (and scheduling appointments) with radiation and medical oncology, dentistry, and oral surgery in a manner that optimizes adherence to the following care delivery processes associated with timely PORT.

- (1) Prior to surgical resection, the patient has consultation with a radiation oncologist at the facility where the patient intends to receive PORT.
- (2) Prior to surgical resection, the patient has a consultation with a dentist and oral surgeon (if indicated) and subsequently undergoes extraction of indicated teeth at the time of surgical resection.
- (3) Engaging with the pathologist if the pathology report is not issued by postoperative day 8. Upon receipt of the pathology report, promptly communicating key pathologic findings to the HN team to facilitate formation of a plan for pathology-directed adjuvant therapy.

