- (4) Scheduling appointments with radiation oncology +/- medical oncology within 10 days of surgery as directed by the HN team.
- (5) Ensuring that the postoperative appointment with radiation oncology is scheduled within 10 days of when the referral was placed.

Function 7: Track referrals to ensure timely scheduling of appointments and patient attendance across fragmented healthcare systems.

Form: Referral and appointment tracking to ensure timely scheduling of appointments and patient attendance. The NDURE navigator systematically tracks referrals or appointments to ensure that clinical encounters necessary for PORT are scheduled in a timely fashion by providers and attended by patients. The NDURE navigator will attempt to adjust appointments to enhance timely PORT and reschedule appointments that are missed by patients or need to be altered to reflect changes in the treatment timeline (e.g. hospital readmission). Referral tracking is documented in an EMR-based patient timeline.

NDURE is a Navigation-Based, Multilevel Intervention Targeting Barriers to Timely, Guideline-Adherent Postoperative Radiation Therapy Following Surgery for Head and Neck Squamous Cell Carcinoma		
Level	Determinant of Timely, Guideline-Adherent PORT	NDURE Intervention Component
Patient	 Lack of patient knowledge about timely, guideline-adherent PORT and associated care processes: beliefs about PORT delay	 Patient education using NDURE Patient Resource Guide
	 Travel burden for cancer care	 Travel support
Team	 Unclear communication between patient and providers regarding intentions and goals for timely, guideline-adherent PORT	 Standardized process for initiating discussion of expectation for PORT
	 Insufficient care coordination between healthcare teams during care transitions and about treatment sequela	 NDURE PORT Care Plan
Organization	 Fragmentation of care across healthcare organizations	 Referral tracking and follow-up
	 Ambiguity about professional role and identity	 Environmental Restructuring

Figure 3: NDURE is a navigation-based, multilevel intervention targeting determinants of timely, guideline-adherent PORT following surgery for head and neck squamous cell carcinoma with intervention components at the patient (light green), healthcare team (light blue), and organizational-levels (dark blue)

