Process for Discussing Need for PORT	Standardized discussion of expected indication for PORT and choice of radiation facility at initial consultation. At the initial surgical consultation, the clinician informs the patient that based on his/her clinical stage, it is expected that treatment will include a package of surgery and PORT. At this same clinical encounter, the NDURE navigator facilitates a discussion with the patient and clinician to help the patient decide at which facility he/she will receive PORT.	Variable discussion of expected indication for PORT without discussion of choice of radiation facility at initial consultation. At the initial surgical consultation, the clinician may inform the patient that based on his/her clinical stage, it is expected that treatment will include a package of surgery and PORT. The head and neck team does not discuss with the patient the choice of the facility at which the patient will receive PORT prior to surgery.
EMR documentation	NDURE PORT Care Plan. At each navigation encounter, the NDURE navigator meets with the patient, caregiver, and clinicians to generate (and update) a PORT Care Plan. The NDURE PORT Care Plan is an EMR-	N/A. Throughout the course of treatment, there is no dedicated documentation in the EMR about (a) clinical factors and care

	
based document that (a) captures clinical factors and the care delivery processes necessary to start PORT; (b) describes the patient's barriers to timely PORT; and (c) documents the patient's personalized Barrier Reduction Plan.
	
delivery processes necessary to start PORT; (b) barriers to timely PORT; or (c) plans to address barriers to timely PORT.

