Referral and Appointment Tracking	
Referral and appointment tracking to ensure timely scheduling of appointments and patient attendance. The NDURE navigator systematically tracks referrals or appointments to ensure that clinical encounters necessary for PORT (e.g. radiation and medical oncology, dentistry, and oral surgery) are scheduled in a timely fashion by providers and attended by patients. The NDURE navigator contacts patients prior to PORT-related appointments to promote attendance, confirms attendance at PORT-related appointments, adjusts the timing of appointments to enhance timely PORT, and reschedules appointments that are missed by patients or need to be altered to reflect changes in the treatment timeline (e.g. hospital readmission). Referral tracking is documented in an EMR-based patient timeline.
	
N/A. Members of the head and neck oncology team (including the nurse navigator) do not systematically track referrals or appointments to ensure that the clinical encounters necessary for PORT are scheduled in a timely fashion by providers, attended by patients, adjusted to enhance timely PORT, or re-scheduled to reflect changes in the treatment timeline.

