8.4.6 CANCER CARE DELIVERY PROCESS ASSESSMENTS

A Cancer Care Delivery Process form is included as the eCRF and will be completed by the program coordinator using information from the EMR.

Pre-Surgical Radiation Consultation is defined as the attendance by the patient at a consultation with the treating radiation oncologist (at MUSC or elsewhere) prior to surgery to discuss RT in the definitive or adjuvant setting. Patients who see a radiation oncologist at one facility prior to surgery but receive PORT at a different facility are evaluated as 'no' for this measure.

Pre-Radiation Therapy Dental Evaluation is defined as the evaluation by a dentist for pre-radiation dental extractions. Edentulous patients are non-evaluable for this measure. Dentulous patients who do not have a pre-surgical dental evaluation are evaluated as 'no'.

Pre-Radiation Extractions of Indicated Teeth with Definitive Surgery is defined as the extraction of indicated carious/non-restorable teeth either prior to or during definitive surgery. Patients who have a dental evaluation that indicates the need for extractions, but for whom teeth are not extracted prior to or during

surgery are evaluated as 'no' for this measure. Edentulous patients and dentulous patients who have a dental evaluation and extractions are not recommended are not evaluable for this measure.

Time from Surgery to Pathology Report is defined as the production of the pathology report from the definitive surgical procedure within the EMR. Addenda to the pathology report at the request of the HNSCC team (e.g. tumor p16 status) are not counted in this measure.

Time from Surgery to PORT Referral is defined as the time, in days, from the date of the definitive surgical procedure to the date the referral (or postoperative appointment) is placed to discuss adjuvant therapy with the treating radiation oncologist. For patients who have seen a radiation oncologist prior to surgery, this metric refers to the scheduling of the post-operative follow-up appointment with the radiation oncologist. In situations in which a patient is re-referred postoperatively (i.e., a patient is referred to a radiation oncologist at one facility and then decides to get treatment at a different facility), the measure is evaluated using the time to the second referral.

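### Some care-process endpoints (outside dental evaluation, outside extractions before surgery, referral date) may be captured differently by arm, because NDURE itself adds to the EMR from which they are abstracted

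*Combined protocol and SAP*

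**What the plan says.** **Data source.** Section 8.4.6 says the Cancer Care Delivery Process form "will be completed by the program coordinator using information from the EMR".

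**What NDURE adds to that record.** Section 6.1.1.1 describes an EMR-based PORT Care Plan that "captures clinical factors and the care delivery processes necessary to start PORT". Of the navigator's appointment tracking it says: "Referral tracking is documented in an EMR-based patient timeline". Table 3 adds that the navigator "confirms attendance at PORT-related appointments".

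**What usual care has.** Table 3 says that "there is no dedicated documentation in the EMR about (a) clinical factors and care" delivery processes, and that team members "do not systematically track referrals or appointments to ensure that the clinical encounters necessary for PORT are scheduled in a timely fashion by providers". Residents, advanced practice providers and nurses do make the referrals and appointments.

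**Scoring.** Section 8.4.6: "Dentulous patients who do not have a pre-surgical dental evaluation are evaluated as 'no". There is no code for an evaluation that may have taken place but is not documented. Section 9.4.2 has no missing-data rule for pre-surgical consultation, dental evaluation or extraction. It also has none for a patient who started PORT but has no recorded referral date.

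**Other records.** A footnote to Table 1, which covers both arms, says that after PORT "the study coordinator will gather all of the required source documentation to ascertain efficacy and cancer care delivery endpoints". Section 8.3 calls for records of care received outside MUSC. Section 8.4.4, written for the efficacy assessments, requests records from the treating facility when adjuvant therapy ends.

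**The concern.** One arm receives, as part of its treatment, a log of the same steps that are later abstracted as outcomes. If the abstractor draws on that log, the chance that a given event is found depends on allocation. The trial is unblinded, no blinded abstraction is described, and nothing stops the navigator's timeline from serving as a source.

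At stake is the secondary objective on cancer care delivery processes. If those endpoints improve under NDURE, the reader needs to know that care changed and not only the charting. The pilot is also meant to inform a definitive trial (Section 4.2.2).

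**Working it through.** **Step 1. Which endpoints are exposed after the record collection in Sections 1.3, 8.3 and 8.4.4?**

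| Endpoint | Where an independent record should exist | Remaining exposure |
|---|---|---|
| Pre-surgical radiation consultation | Treating facility; Section 8.4.6 counts only a visit with the treating radiation oncologist | Small |
| Postoperative radiation oncology appointment | Treating facility | Small |
| Extraction during definitive surgery | MUSC, because the dental sets in Section 9.3 require surgery there | Small |
| Extraction done outside before surgery | Outside dental or oral surgery record, not named in the plan | Yes |
| Dental evaluation by an outside dentist | Dental record, not named in the plan | Yes; absence is scored 'no' |
| Date referral placed | Referral order or fax, not named in the plan | Yes; no rule if the date is missing |
| PORT delay (primary) | PORT start date | Not reached by this point |

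**Step 2. Direction.** A missed usual-care dental visit scored 'no' favours NDURE. Two rules in Section 8.4.6 can work the other way. After a re-referral the second referral is used, so better logging gives NDURE a later date. An extraction indication that is documented but not acted on is a 'no', whereas an undocumented indication drops out of the denominator.

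**Step 3. Size, as an illustration.** The plan gives no power or capture rate for these endpoints. As a check on the test formula, its primary-endpoint figure was reproduced first: 75 per arm, 45% versus 25%, two-sided 0.10, pooled z-test gives 82.7%, against 83% stated in Section 9.2.2.

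Inputs:
- True event rate 60% in both arms (assumed).
- Share of care crossing systems 51% (Section 2.2.5, a background figure on care transitions that is not specific to dental visits or referral orders).
- Inside care fully captured in both arms (assumed).
- Outside events captured 95% in NDURE and 85%, 75% or 65% in usual care (assumed).
- Unrecorded events counted as 'no'.

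Observed rate = 0.60 × 0.49 + 0.60 × 0.51 × capture.

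- NDURE: 0.294 + 0.306 × 0.95 = 58.5%.
- Usual care: 0.294 + 0.306 × 0.85 = 55.4%; with 0.75, 52.4%; with 0.65, 49.3%.
- Spurious difference = 0.306 × gap = 3.1, 6.1 and 9.2 points for gaps of 10, 20 and 30 points.

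Probability that the pooled z-test rejects at nominal two-sided 10% when there is no true effect:

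| Per arm | Gap 0 | Gap 10 | Gap 20 | Gap 30 |
|---|---|---|---|---|
| 85 (170 enrolled) | 10% | 12.7% | 20.6% | 33.0% |
| 75 | 10% | 12.4% | 19.4% | 30.4% |
| 40 (assumed) | 10% | 11% | 15% | 21% |

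The 40-per-arm row is the closest to the dental endpoints. Edentulous patients are not evaluable, and the extraction set is a further subset (Sections 8.4.6 and 9.3), so 75 to 85 per arm is too many for them. The documents do not give the actual number. No figure is offered for time to referral, because the documents give no basis for one.

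**The case against.** The strongest reply is that the plan already handles this. The Table 1 footnote promises source documentation for exactly these endpoints in both arms. The endpoints are defined by events, not by navigator entries, and no sentence makes the Care Plan or timeline a source. Much of this stands. It is why radiation consultation and appointment dates are only weakly exposed, and why extractions during surgery are too. It does not settle the rest: the footnote does not say what documentation is required, and none of the three provisions names a dental provider or the referral order.

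A reader might also infer four stronger things that the documents do not support.
- *That usual care leaves referrals and visits unrecorded.* Table 3 denies only dedicated documentation and systematic tracking, and usual-care staff do place referrals.
- *That the bias always favours NDURE.* The re-referral and extraction rules can push against it.
- *That the evidence on how NDURE works is undermined.* Table 2 and Section 8.4.7 assign mechanism to the health behavior constructs; care processes are a separate objective.
- *That the false-positive rate is known to be inflated to around 30%.* That needs a 30-point gap and full-size arms. With equal capture the rate stays at its nominal level.

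It is also fair to note that Table 2 does not list dental evaluation among the care-process endpoints. Section 9.4.4.2 nevertheless plans a between-arm comparison of it.

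**Conclusion.** The point holds in a limited form. Followed as written, Section 8.4.6 allows ascertainment to depend on arm for outside dental evaluation, extractions done outside before surgery, and the referral-placed date. These are secondary measures.

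The size is unknown. On the stated assumptions the dental evaluation rate would be distorted by about 3 to 9 points. At an assumed 40 per arm, the false-positive rate at nominal 10% would be 11% to 21%. If the gathered source documents equalise capture, there is no distortion. The change is worth making because the plan does not ensure that equality and could do so cheaply.

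**What to change.** In Section 8.4.6:

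1. State that the PORT Care Plan and the navigator timeline are not source documents for any endpoint.
2. Name for each endpoint one provider-level source that exists in both arms: time-stamped referral order, facility visit record, or dental record. Have the coordinator seek it by the same procedure in both arms, including from outside dental providers.
3. Record 'not documented' separately from 'no'. Keep 'no' as the main scoring, report data source and 'not documented' counts by arm, and add a sensitivity analysis treating 'not documented' as missing.

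Two tempting additions should be left out. Requiring confirmed absence before scoring 'no' can itself create bias. Assume a 60% true rate, events captured 95% in both arms, and absences confirmed 95% in NDURE but 75% in usual care. Usual care then shows 0.57 / (0.57 + 0.30) = 65.5%, while NDURE shows 0.57 / (0.57 + 0.38) = 60%. Relying on the predicted-MUSC stratum does not help either, because planning radiation at MUSC does not place the dentist there.

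The cost is a few more record requests and one sensitivity analysis.
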